### 5.2.7. Definition of on-treatment period

Safety endpoints will be summarized based on the on-treatment period unless otherwise specified.

On-treatment period is defined as the time from the first dose of study treatment through minimum (30 days + last dose of study treatment, start day of new anti-cancer drug therapy – 1 day).

Safety data collected outside the on-treatment period as described above will be listed and flagged in listings but will not be summarized.

### 5.2.8. Standard derivations and reporting conventions

The following conversion factors will be used to convert days into weeks, months or years: 1 week = 7 days, 1 month = 30.4375 days, 1 year = 365.25 days.

Demographics and physical measurements:

- Age [years]:
  - (date of given informed consent - date of birth + 1) / 365.25;
  - In case of missing day, day only: Age [years]: (year/month of given informed consent – year/month of birth);
  - In case only year of birth is given: Age [years]: (year of given informed consent - year of birth).

The integer part of the calculated age will be used for reporting purposes.

- BMI (kg/m^2) = weight (kg)/[height (m)]

- $BSA (m^2) = ([\text{height (cm)} \times \text{weight (kg)}] / 3600)^{0.5}$

For reporting conventions, mean and median should generally be displayed one more decimal place than the raw data and standard deviation should be displayed to two more decimal places than the raw data. Percentages will be reported to one decimal place. The rounding will be performed to closest integer / first decimal using the common mid-point between the two consecutive values. Eg, 5.1 to 5.4 will be rounded to an integer of 5, and 5.5 to 5.9 will be rounded to an integer of 6.

### **5.2.9. Unscheduled visits**

Generally, data collected at unscheduled visits will be included and analyzed for both safety and efficacy analyses in the same fashion as the data collected at scheduled visits except where otherwise noted in the sections that follow. Descriptive statistics (mean, SD, median, minimum, maximum, quartiles) by nominal visit or time point for safety endpoints such as laboratory measurements, ECGs and vital signs will include only data from scheduled visits.

### **5.2.10. Adequate baseline tumor assessment**

Adequate baseline is defined using the following criteria:

- All baseline assessments must be within 28 days prior to and including the date of randomization;
- All documented lesions must have non-missing assessments (ie, non-missing measurements for target lesions and non-missing lesions assessment status at baseline for non-target lesions).

### **5.2.11. Adequate post-baseline tumor assessment**

An adequate post-baseline assessment is defined as an assessment where a response of uCR, uPR, SD, non-uCR/non-PD, or PD can be determined (see Section 6.2.2.8). Time points where the response is not evaluable (NE) or no assessment was performed will not be used for determining the censoring date.

## **5.3. Methods to Manage Missing Data**

### **5.3.1. Missing data**

Unless otherwise specified, all data will be evaluated as observed, and no imputation method for missing values will be used.

In all patient data listings imputed values will be presented. In all listings imputed information will be flagged.

Missing statistics, eg when they cannot be calculated, should be presented as 'ND' or 'NA'. For example, if N=1, the measure of variability (SD) cannot be computed and should be presented as 'ND' or 'NA'.

### **5.3.1.1. Pharmacokinetic concentrations**

#### **Concentrations Below the Limit of Quantification**

For all calculations, figures and estimation of individual pharmacokinetic parameters, all concentrations assayed as below the level of quantification (BLQ) will be set to zero. In log-linear plots these values will not be represented. The BLQ values will be excluded from calculations of geometric means and their CIs. A statement similar to ‘All values reported as BLQ have been replaced with zero’ should be included as a footnote to the appropriate tables and figures.

#### **Deviations, Missing Concentrations and Anomalous Values**

In summary tables and plots of median profiles, concentrations will be set to missing if one of the following cases is true:

1. A concentration has been reported as ND (ie, not done) or NS (ie, no sample);
2. A deviation in sampling time is of sufficient concern or a concentration has been flagged as anomalous by the clinical pharmacologist.

Summary statistics will not be presented at a particular time point if more than 50% of the data are missing. For analysis of pharmacokinetic concentrations, no values will be imputed for missing data.

### **5.3.1.2. Pharmacokinetic parameters**

Actual or nominal PK sampling time will be used for the derivation of PK parameters. If a PK parameter cannot be derived from a patient’s concentration data, the parameter will be coded as NC (ie, not calculated). NC values will not be generated beyond the day that a patient discontinues.

In summary tables, statistics will be calculated by setting NC values to missing. Statistics will not be presented for a particular treatment if more than 50% of the data are NC. For statistical analyses (ie, analysis of variance), PK parameters coded as NC will also be set to missing.

If an individual patient has a known biased estimate of a PK parameter (due for example to a deviation from the assigned dose level), this will be footnoted in summary tables and will not be included in the calculation of summary statistics or statistical analyses.

## **5.3.2. Handling of incomplete dates**

### **5.3.2.1. Disease history**

Incomplete dates for disease history (eg, initial diagnosis date, date of documented, locally advanced, inoperable or metastatic disease diagnosis, date of response or progression in prior treatment) will be imputed as follows:

- If the day is missing, it will be imputed to the 15th day of the month.

- If both day and month are missing and the year is prior to the year of the first study treatment, the month and day will be imputed as July 1st.
- If both day and month are missing and the year is same as the year of the first study treatment, the month and day will be imputed as January 1st.
- If the date is completely missing, no imputation will be performed.

### 5.3.2.2. Adverse events

Incomplete AE-related dates will be imputed as follows:

- If the AE onset date is missing completely, then the onset date will be replaced by the start of study treatment.
- If only the day part of the AE onset date is missing, but the month and year are equal to the start of study treatment, then the AE onset date will be replaced by the start of study treatment. For example, if the AE onset date is --/JAN/2015, and study treatment start date is 15/JAN/2015, then the imputed AE onset date will be 15/JAN/2015.
- If both the day and month of the AE onset date are missing but the onset year is equal to the start of study treatment, then the onset date will be replaced by the start of study treatment. For example, if AE onset date is --/--/2014, and study treatment start date is 19/NOV/2014, then the imputed AE onset date will be 19/NOV/2014.
- In all other cases the missing onset day or missing onset month will be replaced by 1.
- Incomplete stop date will be replaced by the last day of the month (if day is missing only), if not resulting in a date later than the date of patient's death. In the latter case the date of death will be used to impute the incomplete stop date.
- In all other cases the incomplete stop date will not be imputed. If stop date of AE is after the date of cut-off outcome of AE is ongoing at cut-off.

### 5.3.2.3. Prior and concomitant medications

Incomplete prior/concomitant medication dates will be imputed as follows:

- If the medication date is missing completely, then the medication date will be replaced by the start of study treatment.
- If the day of medication date is missing, but the month and year are equal to the start of study treatment, then the medication date will be replaced by the start of study treatment. For example, if the medication start date is --/JAN/2015, and study treatment start date is 15/JAN/2015, then the imputed medication start date will be 15/JAN/2015.
- If both the day and month of medication start date are missing but the start year is equal to the start of study treatment, then the medication date will be replaced by the start of study treatment. For example, if the medication start date is --/--/2014, and study treatment start date is 19/NOV/2014, then the imputed medication start date will be 19/NOV/2014.

- In all other cases the missing medication day or missing medication month will be replaced by 1.
- Incomplete stop date will be replaced by the last day of the month (if day is missing only), if not resulting in a date later than the date of patient's death. In the latter case the date of death will be used to impute the incomplete stop date.
- In all other cases the incomplete medication stop date will not be imputed.

#### **5.3.2.4. Exposure**

No imputation will be done for first dose date. Date of last dose of study drug, if unknown or partially unknown, will be imputed as follows:

- If the last date of study drug is completely missing and there is no End of Treatment eCRF page and no death date, the patient should be considered to be ongoing and use the cut-off date for the analysis as the last dosing date;
- If the last date of study drug is completely or partially missing and there is EITHER an End of Treatment eCRF page OR a death date available (within the cut-off date), then imputed last dose date is:
  - = 31DECYYYY, if only Year is available and Year < Year of min (EOT date, death date)
  - = Last day of the month, if both Year and Month are available and Year = Year of min (EOT date, death date) and Month < the month of min (EOT date, death date)
  - = min (EOT date, death date), for all other cases.

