2.	End of Treatment/Withdrawal: Visit to be performed within 3 days following the last dose of study treatment received. Obtain these assessments if not completed within 7 days prior to the EoT/Withdrawal visit, except for tumor assessments and patient-reported outcome questionnaire assessments, which need not be repeated if they have been performed within the prior 6 and 4 weeks, respectively. Patients who complete the maintenance phase and proceed to follow up will follow the prespecified timelines described in the table above. EoT/Early withdrawal imaging (if more than 6 weeks ago) and questionnaire assessments (if more than 4 weeks ago) relate only to patients who discontinue early, and refuse follow up.
3.	Short- and Long-Term Follow-up: All patients will be followed for safety with evaluations at 30 days after the last study treatment administration or until the time of initiation of new systemic anticancer treatment. The Day 90 Short-Term Follow-up Visit will be conducted as a phone call. If any concern arises, the patient will be called in for a follow-up visit within 5 calendar days for appropriate assessments (as per the investigator's medical judgement). Beyond the Day 90 Short-Term Follow-up Visit, all patients will be followed every 16 weeks (Q16W) for survival (additional survival follow up information may be requested) and new systemic anticancer treatment within the long-term follow-up period. Patients who refuse to return to the site for evaluations should be contacted by telephone as an alternative.
4.	Physical Examination: Includes an examination of major body systems and weight.
5.	Vital Signs: Vital signs to include blood pressure and pulse rate. Blood pressure and pulse rate should be taken with the patient in the seated position after the patient has been sitting quietly for at least 5 minutes.
6.	Hematology, Blood Chemistry, and Coagulation: Hematology and core blood chemistry to be performed prior to each administration of avelumab/placebo, and at the EOT/Withdrawal and 30-day Short Term Follow-Up visits. Coagulation to be performed when clinically indicated. Full chemistry panel is required at End of Treatment/Withdrawal. All laboratory assessments may be performed and results reviewed by the treating physician up to 1 business day prior to study drug administration.

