### **Start and end dates of study treatment:**

The date/time of first dose of study treatment is the earliest date/time of the first non-zero dose date/time for each of the study drugs.

The date/time of last dose of study treatment is the latest date/time of the last non-zero dose date/time for each of the study drugs.

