YYYY = Year of min [max(PD date + 1, last dose of study treatment + 1), end date of new anti-cancer therapy], AND

```
MMM = Month of min [max(PD date + 1 day, last dose of study treatment + 1
day), end date of new anti-cancer therapy]
THEN
    imputed start date = min [max(PD date + 1 day, last dose of study treatment + 1
day), end date of new anti-cancer therapy]);
ELSE IF
    YYYY = Year of min [max(PD date + 1, last dose of study treatment + 1), end
date of new anti-cancer therapy], AND
    MMM > Month of min [max(PD date + 1 day, last dose of study treatment + 1
day), end date of new anti-cancer therapy]
THEN
    imputed start date = 01 MMM YYYY;
ELSE IF
    YYYY < Year of min [max(PD date + 1, last dose of study treatment + 1), end
date of new anti-cancer therapy]
THEN
    imputed start date = DAY (Last day of MMM) MMM YYYY;
ELSE IF
    YYYY > Year of min [max(PD date + 1, last dose of study treatment + 1), end
date of new anti-cancer therapy]
THEN
    imputed start date = 01 MMM YYYY.
```

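### SAP 5.3.2.4 has no branch for a last-dose date with a known month in an earlier calendar year, so the End of Treatment or death date overwrites the recorded month

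*SAP*

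**What the plan says.** SAP 5.3.2.4 (Exposure) gives three outcomes for a missing or partial last-dose date when an EOT page or a death date is available. Call the earlier of the EOT and death dates the reference date.

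- Year only: "31DECYYYY, if only Year is available and Year < Year of min (EOT date, death date").
- Year and month: "Last day of the month, if both Year and Month are available and Year = Year of min (EOT date, death date"), with the further condition that the recorded month precedes the reference month.
- Everything else: "min (EOT date, death date), for all other cases".

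SAP 5.3.3.4 handles incomplete start dates of new anti-cancer therapy. When year and month are known and the recorded year is before the reference year used there, it gives "imputed start date = DAY (Last day of MMM) MMM YYYY".

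The imputed date is carried forward. SAP 3.4.1 states: "The date/time of last dose of study treatment is the latest date/time of the last non-zero dose date/time for each of the study drugs". The on-treatment period in SAP 5.2.7 ends at "minimum (30 days + last dose of study treatment, start day of new anti-cancer drug therapy" minus one day). On EOT timing, footnote 2 to Table 3 of the protocol's Schedule of Activities says: "Visit to be performed within 3 days following the last dose of study treatment received".

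**The concern.** A last dose recorded as November 2018, with EOT in 2019, is not year-only, so the first branch does not apply. Its year differs from the reference year, so the second does not apply either. It goes to the catch-all, and the recorded month and year are discarded.

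This looks like an oversight rather than a cautious convention. Elsewhere the three branches give the latest date that is consistent with the record and not after EOT or death. Only here does the result contradict the record. More information also gives a worse answer: with EOT on 15 February 2019, a record of 2018 alone gives 31 December 2018, while November 2018 gives 15 February 2019.

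The error runs in one direction, because the reference date lies in a later year than the record. It can reach:

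- the on-treatment period, and with it treatment-emergent adverse events and on-treatment laboratory, vital-sign and ECG summaries (SAP 3.5.1, 5.2.7, 6.6);
- the immune-related event window of 90 days after last dose, which applies regardless of new anti-cancer therapy (SAP Appendix 1, Table 24);
- deaths within 30 days of last dose (SAP 6.6.2);
- duration of exposure for avelumab/placebo and cisplatin (SAP 6.5.3.1, 6.5.3.2);
- imputed start dates of new anti-cancer therapy, which use last dose plus one day and set censoring in sensitivity efficacy analyses (SAP 5.3.3.4).

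**Working it through.** The plan states no figure to reproduce; the check is on the logic of the date rule. Inputs are the three branches of SAP 5.3.2.4 as written, and a comparison rule that differs only in its second branch: last day of the recorded month whenever the recorded year and month together precede those of the reference date.

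**Coverage.** Three earlier years × 12 recorded months × 12 reference months = 432 combinations. Under the SAP text all 432 return the reference date. A same-year control (March 2018, EOT 10 May 2018) gives 31 March 2018 under both rules.

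**Size.** Excess = SAP date − corrected date. The calendar dates are illustrative assumptions.

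| Recorded last dose | Reference date | SAP gives | Corrected | Excess |
|---|---|---|---|---|
| Dec 2018 | EOT 3 Jan 2019 | 3 Jan 2019 | 31 Dec 2018 | 3 days |
| Nov 2018 | EOT 15 Jan 2019 | 15 Jan 2019 | 30 Nov 2018 | 31 + 15 = 46 days |
| Nov 2018 | EOT 15 Feb 2019, after a hold | 15 Feb 2019 | 30 Nov 2018 | 31 + 31 + 15 = 77 days |
| Nov 2018 | Death 10 Mar 2020, no EOT page | 10 Mar 2020 | 30 Nov 2018 | 31 + 365 + 70 = 466 days |

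**Bounds.** If EOT falls within 3 days of the true last dose, the largest excess is 3 days. Protocol Table 5 allows up to 12 weeks from the last administration for a Grade 3 toxicity to resolve before permanent discontinuation; with EOT up to 84 days after the true last dose, the largest excess is 84 days.

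**On-treatment end.** In the 46-day case, adding 30 days gives 14 February 2019 instead of 30 December 2018, unless new anti-cancer drug therapy starts earlier.

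**30-day deaths.** In the death-only path the imputed last dose equals the death date. The interval is 0 days, so the death always counts as within 30 days.

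**Single-drug exposure.** SAP 6.5.3.2 defines cisplatin duration in weeks as (last dose − first dose + 21)/7. Assume first dose 30 October 2017, last dose recorded as December 2017, and an EOT date for overall treatment of 5 January 2019.

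- Corrected: (62 + 21)/7 = 11.9 weeks.
- As written: (432 + 21)/7 = 64.7 weeks, because the last cisplatin date moves by 370 days.

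**The case against.** The gap in the text is hard to dispute; the case on the other side concerns its consequences, and most of it stands.

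- **Rarity.** Protocol 5.3 has infusions given at the site, with date, time and dose recorded on the eCRF, and the analyses use cleaned data. A case needs a missing day and a change of calendar year before EOT or death.
- **Latest drug governs.** Last dose of study treatment is the latest across drugs. A wrong cisplatin or IMRT date moves the on-treatment end only as far as EOT lies beyond the true last avelumab/placebo dose.
- **Data collection.** A reader might infer from the 466-day example that every adverse event in between becomes treatment-emergent. The documents do not support that. Protocol 8.2 and the Schedule of Activities end routine adverse event recording 90 days after the actual last administration, and earlier for non-serious events if new anticancer therapy starts. After that, SAEs are reported if the investigator learns of them, at minimum those considered related. Since the correct window already covers 30 days, the extra routinely recorded events fall at about days 31 to 90. For the 90-day immune-related window, the addition is mainly late-reported SAEs.
- **Dose intensity is untouched.** It uses fixed durations in the CRT Phase, and the start of the last dosed cycle in Maintenance.
- **Visibility and direction.** Imputed values are flagged in listings, both arms follow the same rule, and a longer window is cautious for attributing adverse events.

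The last point does not rescue the rule. Exposure duration and 30-day deaths are still overstated, and a flag does not correct the summary tables.

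**Conclusion.** The rule is wrong as written for one class of record: month and year known, in a calendar year before the earlier of EOT and death. That follows from the text alone.

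The size depends on the path. The excess is at most 3 days when EOT is on schedule, and weeks when EOT is late or follows a hold. It passes a year for the on-treatment period only with a death date and no EOT page, or a very late EOT. It would be tempting to treat an extension of weeks to more than a year as the usual result; the protocol's 3-day EOT timing does not support that. The on-treatment period is also capped by the start of new anti-cancer drug therapy.

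Adverse event misclassification is confined mainly to events about 31 to 90 days after the true last dose, plus later-reported SAEs. The 30-day death count and per-drug exposure duration do not have that limit. Few patients are likely to be affected, but this is a judgement, since no count is given. Primary PFS and OS do not use the last-dose date and do not change; in efficacy, only sensitivity analyses that rely on an imputed new-therapy start date could move.

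**What to change.** Rewrite the second branch of SAP 5.3.2.4 so that it gives the last day of the recorded month when year and month are both known and either (a) the recorded year is before the year of the earlier of EOT and death, or (b) the years are equal and the recorded month is before that date's month. Leave the other two branches as they are. This brings the rule into line with SAP 5.3.3.4.

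The cost is one line of the SAP and the matching line of code. It needs no new data, leaves the primary endpoint and its analysis unchanged, and can be done before database lock. Without it, a programmer must either code a date known to contradict the eCRF or depart from the SAP.

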#### **5.3.3. Imputation rules for date of last contact and efficacy assessments**

##### **5.3.3.1. Date of last contact**

The date of last contact will be derived for patients not known to have died at the analysis cut-off using the latest complete date among the following:

- All patient assessment dates (blood draws (laboratory, PK), vital signs, performance status, ECG, tumor assessments);
- Start and end dates of anti-cancer therapies administered after study treatment discontinuation;
- AE start and end dates;
- Last date of contact collected on the 'Survival Follow-up' eCRF (do not use date of survival follow-up assessment unless status is 'alive');
- Study drug start and end dates;
- Randomization date;
- Withdrawal of consent date;

- Date of discontinuation on disposition eCRF pages (do not use if reason for discontinuation is lost to follow-up).

Only dates associated with actual examinations of the patient will be used in the derivation. Dates associated with a technical operation unrelated to patient status such as the date a blood sample was processed will not be used. Assessment dates after the cut-off date will not be applied to derive the last contact date.

### **5.3.3.2. Death date**

Missing or partial death dates will be imputed based on the last contact date:

- If the date is missing it will be imputed as the day after the date of last contact
- If the day or both day and month is missing, death will be imputed to the maximum of the full (non-imputed) day after the date of last contact and the following:
  - Missing day: 1st day of the month and year of death
  - Missing day and month: January 1st of the year of death

